- b) Baseline visit (Consent, Final eligibility, baseline data collection and product provision): Participants will receive a study overview. Informed consent for the study will be obtained. Final in-person eligibility will be confirmed with an exhaled carbon monoxide via Bedfont Micro Smokerlyzer. Participants meeting final eligibility will be enrolled in the study. Baseline data collection will immediately follow screening at the same visit. Measures will be completed per the schedule of measures above (see Table 1), broadly including: recent CC and EC use, cigarette dependence; respiratory symptoms; intentions to quit smoking; and biomarkers of tobacco use and inflammation. Biological assessments involving urine sample collection will be performed by the RA.
Following completion of all scheduled measures, participants will be provided with a complimentary NJOY ACE device, information on its storage and use, and disposable cartridges in the tobacco flavor. Participants will be provided with a number of pods comparable to 150% of their weekly consumption of nicotine based on their responses to the baseline timeline follow-back (TLFB). This quantity will ensure that participants have adequate pods to fully substitute combustible cigarettes within a reasonable margin of error (e.g., timing/scheduling of the next session) should they choose to do so. As each standard 5% NJOY ACE pod provide an amount of serum nicotine delivery in ideal use conditions comparable to one pack of cigarettes (i.e., 20 cigarettes), we will compute participants' average weekly cigarette consumption in packs and provide 1.5x that number of cartridges.
- c) Phone call visits at Weeks 1 and 3: These visits will be conducted by phone. Participants will be assessed for their cigarette, tobacco, and EC use. Participants will also be assessed for any quit attempt or adverse event and will be asked for any issues using the product and reminded to use the EC instead of the CC every time they want to smoke.
- d) In person Visit at Week 2: Participants will attend an in-person visit at Week 2 to receive a new 2-week supply of pods, return used and unused pods to measure EC use, complete assessments and troubleshoot device or other study-related issues.
- e) In person Visit at Week 4: Participants will attend an in-person visit at Week 4 when product provision will end and all baseline assessments will be repeated.

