- f) Exit Qualitative interviews: A purposive subsample of 8 trial participants (4 who switched fully or partially to EC and 4 who switched minimally or not at all to EC) will receive a semi-structured exploratory qualitative interview at Week 4 to assess study and EC acceptability. Domains include general thoughts about the study procedures, description about EC use

experience (sensation, emotional aspects of use, flavor, taste, smell, side effects, etc.) and barriers to EC use during the study or to continuing EC use.

g) Phone call visit at Week 8: A phone call at Week 8 will assess CC and EC use after product provision ends and repeat other assessments.

Texting for Visit Reminders & Assessments

Participants that consent to receiving text messages will receive messages reminding them of their upcoming in-person visits (baseline in-person visit, week 2 in-person visit, week 4 in-person visit)

Quantitative measures:

a) Measures already collected by Screen ASSIST trial and survey⁶: Sex, age, race/ethnicity, education, past medical history (lung cancer, CVD, COPD), alcohol use screener, tobacco use history (year started, pack-years, CPD, prior quit attempts, quit methods used) self-reported smoking status at end of study and household income.

b) Screener measures: past 30-day CC and EC use, recent quit attempts, quit methods used, plan to quit smoking in the next 30 days.

c) Recent tobacco use and quit attempts: past 7-day CC and EC use, recent quit attempts,

d) Current medical history: self-report of diagnosis of cancer, CVD, COPD and other chronic diseases made by a physician.

e) Alcohol use screener: Audit-C short form.

f) Current CC Use: Assessed with a 7-day timeline follow back interview (TLFB) during in-person or phone visits.²²

g) Current EC Use: We will only quantify EC use as yes vs.no for each day of assessment. We will not quantify the amount of EC use.
--Daily EC use (yes/no) assessed with 7-day TLFB at in-person & phone visits.
--EC pod collection/count: EC use will be estimated with the number of used and unused pods returned at 2 and 4 weeks (end of EC provision).

h) EC and CC related harm perceptions: Measures from PATH to assess absolute and comparative addiction perceptions of EC and CC;²³ the perceived health and addiction risk assessment scales will be used to assess risk associated with nicotine, CC and EC.^{24,25}

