i) EC Acceptability: Subjective effect of EC (e.g. satisfaction, psychological reward, craving reduction) using the modified E-Cigarette Sensory Effects and Appeal Ratings and the Electronic cigarette rating scale⁰;²⁶ beliefs and behaviors related to EC measuring nine positive expectancies and seven negative expectancies related to EC using the Electronic Cigarette Smoking Consequences Questionnaire;²⁷ Participants will also be asked to compare the taste, satisfaction and helpfulness for managing cravings of the study e-cigarette to the usual cigarette they smoked before the study.

j) Cigarette and e-cigarette dependence: Time to First Cigarette and Time to First EC of the Day measured with the Fagerstrom Test of Cigarette Dependence (FTCD);²⁸ and its e-cigarette adaptation.²⁹ Patient Reported Outcomes Measurement Information System (PROMIS) Nicotine Dependence Item Bank.^{30,31} The Penn State electronic cigarette dependence index will also be included to assess e-cigarette dependence.³³

k) Nicotine Withdrawal Symptoms: Minnesota Nicotine Withdrawal Scale (MNWS)³⁴, which assess both the desire to smoke and withdrawal symptoms.

l) Smoking Urges: Questionnaire of smoking urges-brief.³⁵

- m) **Biomarkers of Exposure:** Exhaled breath samples measured as concentration of Carbon Monoxide (CO) in parts per million. Cotinine and Anabasine measured in the urine sample. Cotinine is the major metabolite of nicotine. It is found in both CC and ECs. It will be measured to assess EC safety. Cotinine may or may not change with a CC to EC switch, depending on degree of substitution.³⁶ Anabasine is a tobacco alkaloid that reflects exposure to combustible tobacco products and should fall with reductions in CPD.³⁶ Urine samples will be collected and stored at MGH and analyzed at Mayo Clinic laboratories.
- n) **Respiratory Symptoms:** Assessed with the American Thoracic Society questionnaire.³⁷
- o) **EC Adverse Events:** self-reported adverse events with open-ended questions about new symptoms since the last visit, then symptom checklist of common vaping side effects,

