Remuneration: Remuneration will be provided via gift cards purchased on an MGB Corporate Card. Participants will receive gift cards for their participation. Participants will receive \$50 for attending the baseline in-person visit, \$50 for attending the Week 2 visit, and \$80 for attending the Week 4 in-person visit, and \$30 for a Week 8 phone visit. Participants will receive \$15 for completing the phone visits at Weeks 1 and 3. Total possible compensation is \$240. Compensation will not be contingent on EC or CC use status.

7. Risks and Discomforts

a) *E-cigarette use:*

E-cigarettes are devices that heat nicotine to produce an aerosol that users "vape." The health effects of e-cigarettes are still unclear, but preliminary data suggest that using e-cigarettes is generally less harmful than smoking tobacco cigarettes in that e-cigarettes expose users to fewer toxicants than cigarettes,¹² and emerging data suggest that smokers who switch completely from conventional cigarettes to e-cigarettes will likely reduce their risk of tobacco-related health harms (the goal of the present study). Most exclusive e-cigarette users have lower nicotine levels than when they smoked regular combustible cigarettes. Some e-cigarette users, especially those who use both e-cigarettes and regular tobacco cigarettes, as well as youth and young adults, can have increased nicotine levels, though recent data suggests that on average, exclusive vapers, exclusive cigarette smokers and dual users of both products have similar levels of daily nicotine intake.³⁸ In some rare cases, these use patterns have been associated with seizures. Whether this would occur with individuals instructed to switch completely to e-cigarettes from cigarettes is unclear but based on prior data we would hypothesize highly unlikely to occur in the present study. E-cigarette users very often maintain an addiction to nicotine, but this addiction appears to be somewhat less than that from tobacco cigarettes. Abruptly quitting e-cigarettes could cause withdrawal symptoms similar to those from quitting tobacco cigarettes but slightly less severe. The most common side effects include dry mouth, irritation of the throat and mouth, and mild cough.

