All patients will receive detailed verbal and written instructions (at Baseline) about how to properly use e-cigarettes, safely charge and store the devices, and instructions to reach out to study staff at any time during the study with any questions or concerns about e-cigarette use. To minimize the risks outlined above, we will also instruct patients on the nicotine content of the e-cigarettes compared to their regular daily cigarette and provide e-cigarette pod supplies using this calculation (adjusted as needed), as well as instruct patients on the signs/symptoms of too much or too little nicotine. We will closely monitor for symptoms of nicotine increase from baseline, nicotine overdose or withdrawal, and respiratory symptoms at scheduled visits and in-between visits as necessary. We will advise patients to report all adverse events (assessed at each visit), and arrangements will be made for urgent visits with the patient's primary care provider, our study physicians, or the emergency department depending on the nature of the event. We will exclude individuals with severe medical complications as mentioned above. See Data Safety Monitoring Plan for additional details on safety monitoring and adverse event reporting.

b) Loss of confidentiality: Loss of confidentiality is another potential risk, though unlikely, for questionnaire items. We have never had any confidentiality issues in any of our related trials and overall risks from loss of confidentiality are expected to be minimal. We will ensure that maximal care is taken to preserve participant confidentiality to the highest extent possible. Questionnaire data will be collected and stored electronically using secure systems (e.g. REDCap; Research Electronic Data capture; <http://project-redcap.org>) and questionnaire data will not include any identifying information. Consent forms will be stored in a separate, locked filing cabinet within the PI's locked office on a locked floor at MGH. Additionally, access to patient identifiers will be limited to necessary study staff on a password protected encrypted network drive on MGH's secure server. A separate file will link study ID with patient contact information. All digital audio recordings for the qualitative interviews will be immediately uploaded to the PI's MGH-encrypted computer and the file will then be deleted

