Training of all Study Personnel in the Responsible Conduct of Human Studies: Prior to recruiting subjects or handling study data, all study personnel will be required to pass the NIH approved course that reviews regulatory and informational documents on human subject protection and the responsible conduct of human studies. In addition, all study personnel will sign a statement of commitment to the protection of the rights and welfare of human subjects participating in research.

DATA SAFETY MONITORING PLAN

Overview: The PI will be responsible for monitoring safety throughout the trial and adhering to all reporting requirements. The PI will assume responsibility for reporting all adverse events that may arise to the IRB and/or federal funding agency, as required. Adverse events will be defined according to FDA's definition (i.e., any untoward consequence to study participants that may be related or possibly related to study procedures). Events may include, but are not limited to, worsening of psychiatric, emotional or physical symptoms; breaches in participant confidentiality, deviations from IRB-approved protocols (e.g., contacting participants to obtain survey data outside of IRB-approved time windows), or any participant safety concerns. Study recruitment, enrollment, and retention will be reviewed by the PI and research assistant (RA) weekly. Informed consents will also be reviewed weekly by the RA and PI, and monthly by the PI's mentors for the purposes of quality control. The RA will report on any issues or obstacles in recruitment, enrollment, survey administration, biospecimen collection, e-cigarette provision, and follow-up to the PI during weekly research team meetings. The RA will review all questionnaire and collected biospecimens (e.g., breath, urine) in real time to ensure data completion.

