Safety monitoring plan: In this proposal, we will provide e-cigarettes to individuals who smoke cigarettes who are not ready to quit smoking. We will collect safety information related to the following categories: (1) worsening of respiratory symptoms, (2) symptoms of nicotine toxicity, and (3) adverse events of e-cigarettes previously reported to the FDA. This includes regular monitoring (every 2 weeks for all participants and more if needed determined on a case-by-case basis) of dyspnea and open-ended questions on any medical care (including hospitalizations or emergency room visits) since the last visit assessed at each study visit. While nicotine toxicity is rare in clinical trials, we will monitor breath CO levels at each study visit and also monitor for potential signs and symptoms of nicotine withdrawal. Adverse events related to e-cigarettes previously reported to the FDA include serious events such as hospitalization for pulmonary or cardiac causes, seizure, burns caused by e-cigarette devices/malfunction, and other adverse events such as headache, nausea/vomiting, dizziness, confusion, blurry vision, throat irritation, abdominal pain, and sleepiness. We will advise participants to stop e-cigarette use if necessary. A trained RA will collect all data. In the event of any adverse or other events that require immediate medical, psychiatric or other professional

intervention, the RA will immediately page the PI who will triage the patient to the appropriate emergency services (e.g., 911 or emergency room).

Attribution of adverse events: Adverse events are any side effect that occurs in a participant, while serious adverse events are those that are life-threatening, resulting in hospitalization, disability, or death. We will attribute adverse events that arise in the study to e-cigarettes according to the following scale: definite (clearly related to e-cigarettes), probable (likely related to e-cigarettes), possible (may be related to e-cigarettes), unlikely (likely not related to e-cigarettes), and unrelated (clearly not related to e-cigarettes).

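### The risk section says adverse events are assessed at each visit, but the schedule has no adverse-event question at Week 8, so Weeks 4-8 rely on volunteered reports

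*Combined protocol and SAP*

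**What the plan says.** All references are to the combined protocol and SAP.

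- **Section 7(a), Risks and Discomforts:** "We will advise patients to report all adverse events (assessed at each visit".
- **Section 6, schedule table:** the adverse-event row is marked at Weeks 1, 2, 3 and 4. Week 8 is blank.
- **Section 6, Schedule of Assessments (c), on the Week 1 and 3 calls:** "Participants will also be assessed for any quit attempt or adverse event".
- **Section 6, Schedule of Assessments (g):** "A phone call at Week 8 will assess CC and EC use after product provision ends and repeat other assessments". The item's own label calls this contact a visit, and the Remuneration paragraph offers payment "for a Week 8 phone visit".
- **Section 6, Quantitative measures (o):** the instrument is "self-reported adverse events with open-ended questions about new symptoms since the last visit, then symptom checklist of common vaping side effects".
- **Section 10, Data Safety Monitoring Plan, Overview:** "The PI will be responsible for monitoring safety throughout the trial and adhering to all reporting requirements".
- **Section 10, Safety monitoring plan:** "open-ended questions on any medical care (including hospitalizations or emergency room visits) since the last visit assessed at each study visit".

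Section 3 lists adverse events under the secondary outcome of acceptability and tolerability. It gives the 8-week assessment the job of establishing who still uses e-cigarettes, who has gone back to cigarettes and who uses both.

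**The concern.** The narrative and the schedule give different instructions for the same contact. Staff usually work from the schedule and the forms built on it, so the blank cell is likely to decide what is asked.

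Week 8 is where the trial learns who went on vaping after free supply stopped. As scheduled, those people report their use but are not asked how they have tolerated it. Section 10 starts the clock for reporting a serious event to the IRB when the investigator becomes aware of it. An event nobody asks about may never start that clock. The tolerability information passed to a later, larger trial would also stop at Week 4 without the plan saying so.

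**Working it through.** The plan gives no figure to reproduce. The check is a reading of the schedule against the text, followed by simple counts.

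**1. Is the blank cell real?** Other rows of the same table do carry a mark at Week 8: quit attempts, 7-day cigarette use, 7-day e-cigarette use, risk perceptions and smoking urges. The column is therefore intact, and the adverse-event row stops at Week 4.

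**2. Is Week 8 a visit?** Section 6 calls it one twice, in item (g) and in the Remuneration paragraph. Item (c) also describes the Week 1 and 3 calls as visits.

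**3. Does the Week 8 text fill the gap?** Item (g) promises to repeat other assessments without naming them. The schedule supplies natural candidates (quit attempts, risk perceptions, smoking urges), and adverse events are not among them. Item (c), by contrast, names adverse events for the Week 1 and 3 calls.

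**4. Contacts covered.** Post-baseline contacts in the schedule are Weeks 1, 2, 3, 4 and 8, which is 5. Those with an adverse-event mark are Weeks 1, 2, 3 and 4, which is 4. After supply ends the count is 0 of 1.

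**5. Time covered.** The question looks back to the previous visit, so the marked contacts cover Weeks 0 to 4.
- Time with no scheduled question: (8 − 4) × 7 = 28 days.
- Total follow-up: 8 × 7 = 56 days.
- Share: 28 / 56 = 50%.

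This share follows directly from the visit dates. It measures time without a scheduled question, not events missed.

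**6. Cost of asking.** The minutes per call are an assumption; 30 is the planned enrolment.
- Low: 3 × 30 / 60 = 1.5 staff hours.
- High: 10 × 30 / 60 = 5 staff hours.

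The documents give no event rate for Weeks 4-8, so the number of events that would go unrecorded cannot be estimated.

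**The case against.** The best defence is that the protocol uses the word visit in two senses. The confidentiality text in Section 7(b) says assessment visits take place in person, and the schedule header labels Week 8 a follow-up phone call. On an in-person reading, Section 7(a) sets a minimum, and asking by phone at Weeks 1 and 3 merely exceeds it. Stopping at Week 4 is also a coherent design: the instrument is built around vaping side effects, Weeks 0-4 are grouped as the provision period, and Section 3 lists tolerability separately from product use after provision.

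Part of this stands. The Week 1 and 3 questions do not by themselves prove that Section 7(a) covers phone contacts, and ending the questions with supply would be a legitimate choice. But the plan does not state that choice, and Section 6 expressly calls Week 8 a visit. Even on the in-person reading, Weeks 4-8 have no scheduled question.

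A reader might also infer three stronger points that the documents do not support:

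- **That the medical-care promise in Section 10 is plainly broken at Week 8.** That sentence sets a two-weekly interval, and the next one promises breath carbon monoxide at each study visit, which a phone call cannot deliver. Study visit there may mean the in-person visits, so the wording is ambiguous. The lack of a schedule row settles little, because the question could be asked within the adverse-event interview.
- **That safety monitoring stops at Week 4.** Section 7(a) tells participants to report all events and lets them contact staff throughout the study. The principal investigator's responsibility and the reporting duties in Section 10 continue.
- **That the exit interviews close or measure the gap.** They involve 8 people, concern acceptability, and are dated Week 4 in the text ("will receive a semi-structured exploratory qualitative interview at Week 4 to assess study and EC acceptability") but Week 8 in the schedule. Side effects are one topic within them. They are not adverse-event ascertainment for the cohort.

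**Conclusion.** The point holds as an inconsistency with a practical consequence. The risk section promises adverse-event assessment at each visit, Section 6 calls Week 8 a visit, and the schedule omits the question there. Followed as scheduled, 4 of 5 post-baseline contacts carry the question and the four weeks after supply ends have none. Events in that period would come to light mainly if participants volunteered them.

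The size is modest. Adverse-event questioning in the four supply weeks is complete, no primary outcome is touched, and this is a 30-person pilot. The correction is still worth making, because continued vaping after supply is something the trial sets out to observe and the question costs little. The conclusion rests on taking Section 6's own description of Week 8 as a visit, and on staff following the schedule where it and the narrative differ.

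**What to change.** Add three items to the existing Week 8 call, all covering the time since Week 4: the open-ended adverse-event question, the symptom checklist from Quantitative measures (o), and a question on hospital or emergency care. Mark them in the schedule and name them in Schedule of Assessments (g). Report Week 4-8 events separately from those during provision, because exposure after Week 4 is no longer supplied by the study. Asking the respiratory questionnaire at Week 8 is optional; it is already scheduled for the Week 1 and 3 calls.

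If adverse-event questions are meant to end with supply, Section 7(a) should say so and give the reason. It would also help to state in Section 10 whether study visit means in-person visits only.

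The cost is a few extra minutes on a call that is already scheduled and paid for, in total 1.5 to 5 staff hours under the assumption above, plus a schedule amendment. No new visit or laboratory test is needed.
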